4.3.1.3. Main Analytical Approach

The secondary pharmacokinetic analyses will be based on the PK analysis set in all study parts, unless otherwise specified. Available data will be analyzed as collected regardless of intercurrent events that may occur (treatment policy). Missing data will not be imputed.

Drug concentration measures

Concentrations of sotrovimab in serum through Day 29 and Week 24 will be listed for all participants by actual time and summarized by treatment arm, concentration and nominal time. Standard summary statistics will be calculated (i.e. n, arithmetic mean, 95% CI, standard deviation, median, minimum, maximum, %CV_b, 5th and 95th percentiles). Refer to the R&D Guideline: Non-Compartmental Analysis of Pharmacokinetic Data, GUI_000722 (v6.0), for more information regarding the treatment of serum concentrations that are BLOQ.

Individual serum concentration-time profiles and median/mean profiles by treatment arm and by concentration will be plotted for each participant within one figure both on the untransformed scale (i.e. a linear plot) and on the log transformed scale (i.e. log-linear plot). See [OPS](#) Section 2 List of Data Displays/ TFL Table of Content for details.

Derived Pharmacokinetic Parameters

Parameters will be summarized according to the method defined in Section [4.3.1.1](#) as described below. Individual participant PK parameter values and a descriptive summary will be reported by treatment arm (for all study parts) and by concentration (for Part A only). Data display specifications for derived PK parameter summaries and listings are provided in [OPS](#) Section 2 List of Data Display/ TFL Table of Content.

Table 6 Summary Statistics for Transformed and Untransformed PK Parameters

Untransformed Data: all parameters	n, arithmetic mean, 95% CI for the arithmetic mean, SD, median, minimum, maximum, %CV _b (percent coefficient of variation between subjects)
Log _e -transformed Data: all parameters except for T _{max} , T _{last} , t _{1/2} , and λ _z	n, geometric mean, 95% CI for the geometric mean, SD of log _e -transformed data and %CV _b

The following statistical analyses will also be performed for the following derived PK parameters from evaluable participants. Evaluable participants are defined as those who have sufficient PK concentration data to allow estimation of PK parameters used for secondary endpoint analysis (i.e., AUC_{D1-29} and C_{max}).

Part A:

For Part A, the comparisons of relative bioavailability on Day 29 will be conducted for 100 mg/mL IM sotrovimab at 2 alternative injection sites (anterolateral thigh and deltoid) relative to the 62.5 mg/mL formulation administered dorsogluteally.

1. Injection Site Effect on Relative Bioavailability (for Part A Day 29 SAC)
Endpoint(s)
• C _{max} , AUC _{D1-29}
Model Specification

 log_e-transformed values of endpoints will be statistically analyzed separately using ANCOVA with the following terms: 
 Dependent variable: C_{max}, AUC_{D1-29} Covariates: sex, baseline BMI, treatment (62.5 mg/mL IM sotrovimab into dorsogluteal muscles, 100 mg/mL IM sotrovimab into dorsogluteal muscles,

1. Injection Site Effect on Relative Bioavailability (for Part A Day 29 SAC)

100 mg/mL IM sotrovimab into anterolateral thigh and 100 mg/mL IM sotrovimab into deltoid)

Data will be analyzed for PK Principal Stratum Analysis Set in Part A.

Point estimates and their associated 90% CI will be constructed for the differences in PK parameter values between the test injection sites (100 mg/mL IM sotrovimab [anterolateral thigh], 100 mg/mL IM sotrovimab [deltoid]) and reference injection site (62.5 mg/mL IM sotrovimab [dorsogluteal muscles]). The point estimates and their associated 90% CIs will then be back transformed to provide point estimates and their 90% CIs for the ratios, test/reference in PK parameter values on the original scale.

- The Kenward and Roger method for approximating the denominator degrees of freedom and correcting for bias in the estimated variance-covariance of the fixed effects will be used.

Model Checking & Diagnostics

- For ANCOVA, model assumptions will be checked, and appropriate adjustments may be applied based on the data.
- Distributional assumptions underlying the model used for analysis will be examined by obtaining a normal probability plot of the residuals and a plot of the residuals versus the fitted values (i.e., checking the normality assumption and constant variance assumption of the model respectively) to gain confidence that the model assumptions are reasonable

Model Results Presentation

- Geometric least-squares means for each treatment (100 mg/mL IM sotrovimab into anterolateral thigh, 100 mg/mL IM sotrovimab into deltoid and 62.5 mg/mL IM sotrovimab into dorsogluteal muscles), point estimates and associated 90% CIs for the ratios (100 mg/mL IM sotrovimab [anterolateral thigh]:62.5 mg/mL IM sotrovimab [dorsogluteal muscles], 100 mg/mL IM sotrovimab [deltoid]:62.5 mg/mL IM sotrovimab [dorsogluteal muscles]) for each parameter will be produced in tabular format.
- Comparative plots of individual PK parameters will be generated on linear and semi-logarithmic scales.
- Plots of geometric mean ratio of test to reference treatment (100 mg/mL IM sotrovimab [anterolateral thigh]:62.5 mg/mL IM sotrovimab [dorsogluteal muscles], 100 mg/mL IM sotrovimab [deltoid]:62.5 mg/mL IM sotrovimab [dorsogluteal muscles]) together with 90% CIs will be produced.

In addition, for Part A, the comparisons of relative bioavailability at Week 24 will also be performed for 100 mg/mL IM sotrovimab at 3 injection sites (dorsogluteal, anterolateral thigh, and deltoid) relative to the 62.5 mg/mL formulation administered dorsogluteally.

2. Injection Site Effect on Relative Bioavailability (for Part A Week 24 SAC)

Endpoint(s)

- AUC_{inf}

Model Specification

2. Injection Site Effect on Relative Bioavailability (for Part A Week 24 SAC)

- \log_e -transformed values of endpoints will be statistically analyzed using ANCOVA with the following terms:
 - **Dependent variable:** AUC_{inf}
 - **Covariates:** sex, baseline BMI, treatment (62.5 mg/mL IM sotrovimab into dorsogluteal muscles, 100 mg/mL IM sotrovimab into dorsogluteal muscles, 100 mg/mL IM sotrovimab into anterolateral thigh and 100 mg/mL IM sotrovimab into deltoid)

Data will be analyzed for PK Principal Stratum Analysis Set in Part A.

- Point estimates and their associated 90% CI will be constructed for the differences in PK parameter values between the test treatment (100 mg/mL IM sotrovimab into dorsogluteal muscles, 100 mg/mL IM sotrovimab into anterolateral thigh, 100 mg/mL IM sotrovimab into deltoid) and reference treatment (62.5 mg/mL IM sotrovimab into dorsogluteal muscles). The point estimates and their associated 90% CIs will then be back transformed to provide point estimates and their 90% CIs for the ratios, test/reference in PK parameter values on the original scale.
- The Kenward and Roger method for approximating the denominator degrees of freedom and correcting for bias in the estimated variance-covariance of the fixed effects will be used.

Model Checking & Diagnostics

- For ANCOVA, model assumptions will be checked, and appropriate adjustments may be applied based on the data.
- Distributional assumptions underlying the model used for analysis will be examined by obtaining a normal probability plot of the residuals and a plot of the residuals versus the fitted values (i.e., checking the normality assumption and constant variance assumption of the model respectively) to gain confidence that the model assumptions are reasonable

Model Results Presentation

- Geometric least-squares means for each treatment (100 mg/mL IM sotrovimab into anterolateral thigh, 100 mg/mL IM sotrovimab into deltoid, 100 mg/mL IM sotrovimab into dorsogluteal muscles and 62.5 mg/mL IM sotrovimab into dorsogluteal muscles), point estimates and associated 90% CIs for the ratios (100 mg/mL IM sotrovimab [anterolateral thigh]:62.5 mg/mL IM sotrovimab [dorsogluteal muscles], 100 mg/mL IM sotrovimab [deltoid]:62.5 mg/mL IM sotrovimab [dorsogluteal muscles], and 100 mg/mL IM sotrovimab [dorsogluteal muscles]:62.5 mg/mL IM sotrovimab [dorsogluteal muscles]) for each parameter will be produced in tabular format.
- Comparative plots of individual PK parameters will be generated on linear and semi-logarithmic scales.
- Plots of geometric mean ratio of test to reference treatment (100 mg/mL IM sotrovimab [anterolateral thigh]:62.5 mg/mL IM sotrovimab [dorsogluteal muscles], 100 mg/mL IM sotrovimab [deltoid]:62.5 mg/mL IM sotrovimab [dorsogluteal muscles], and 100 mg/mL IM sotrovimab [dorsogluteal muscles]:62.5 mg/mL IM sotrovimab [dorsogluteal muscles]) together with 90% CIs will be produced.

4.3.2. Safety

4.3.2.1. Estimand

Table 7 Primary Estimand for Secondary Safety Endpoint (Part A)

Primary Estimand	
Population	Male or female healthy participants aged 18 to 65 years
Variable/Endpoints	Incidence of all AEs, SAEs, and AESI through Day 29 ^a /Week 35
Treatment	100 mg/mL IM sotrovimab administered at dorsogluteal, anterolateral thigh, and deltoid injection sites and 62.5 mg/mL IM sotrovimab administered dorsogluteally
Strategy for Intercurrent Events or Events Leading to Missing Data	The intercurrent event of interest is participants receiving incomplete IM dose. The strategy of handling this intercurrent event will be a Treatment Policy Strategy, where all safety data after the intercurrent event will be included. Missing data will not be imputed.
Population-Level Summary	Frequency and percentages of participants

^aDay 29 for anterolateral thigh and deltoid injection sites only as dorsogluteal injection sites are included in the primary safety endpoint.

Table 8 Primary Estimand for Secondary Safety Endpoint (Part C Cohort 1)

Primary Estimand	
Population	Male or female healthy participants aged 18 to 65 years
Variable/Endpoints	Incidence of all AEs, SAEs, and AESI through Week 35 (i.e., all events on the database at the time of DCO)
Treatment	Single IV infusion of sotrovimab at 3000 mg dose
Strategy for Intercurrent Events or Events Leading to Missing Data	The intercurrent event of interest is participants receiving incomplete IV dose. The strategy for handling this intercurrent event will be a Treatment Policy Strategy, where all safety data after the intercurrent event will be included. Missing data will not be imputed.
Population-Level Summary	Frequency and percentages of participants

4.3.2.2. Definition of Endpoint(s)

For Part A, the secondary safety endpoints are:

- Incidence of AEs through Day 29 (100 mg/mL IM sotrovimab administered at anterolateral thigh and deltoid injection sites) and Week 35 (all treatment arms)
- Incidence of SAEs through Day 29 (100 mg/mL IM sotrovimab administered at anterolateral thigh and deltoid injection sites) and Week 35 (all treatment arms)
- Incidence of AESIs through Day 29 (100 mg/mL IM sotrovimab administered at anterolateral thigh and deltoid injection sites) and Week 35 (all treatment arms)

- Incidence of clinically significant changes in vital signs compared to baseline through Day 29 and Week 35
- Incidence of clinically significant laboratory abnormalities through Day 29 and Week 35

For Part C Cohort 1, the secondary safety endpoints are:

- Incidence of AEs through Week 35
- Incidence of SAEs through Week 35
- Incidence of AESIs through Week 35
- Incidence of clinically significant changes in vital signs compared to baseline through Day 29 and Week 35
- Incidence of clinically significant laboratory abnormalities through Day 29 and Week 35

4.3.2.3. Main Analytical Approach

The analyses will be performed using the Safety analysis set in all study parts, as defined in Section 3. Unless otherwise specified, available data will be analyzed as collected regardless of intercurrent events that may occur (treatment policy). Missing data will not be imputed.

Adverse Events, Serious Adverse Events and Adverse Events of Special Interests

Occurrence of AEs, SAEs, and AESIs through Week 35 will be displayed in the form of summaries and listings, where appropriate.

Unless otherwise specified, the secondary safety endpoints will be analyzed as described in Section 4.2.2.2 for the primary safety endpoints.

Vital Signs

Vital sign data include temperature, pulse rate (PR), oxygen saturation (SpO₂), respiratory rate, and blood pressure.

Summary statistics for all results and changes from baseline will be provided in a table by visit for each test. For each test, worst case for each participant will also be summarized by visit. In addition, number of participants with increase in maximum grade from baseline will be summarized by visit for each parameter in a table. A shift table will also be generated to present the shift in post-baseline maximum grade from baseline by visit and overall worst-case post-baseline.

All vital sign data, as well as participants with abnormalities of potential clinical importance and grade will be provided in listings.

Clinical Laboratory Data

Clinical laboratory tests to be performed are listed in Appendix 3. For laboratory tests including hematology, coagulation, clinical chemistry and urinalysis, baseline, post-baseline and change from baseline results will be summarized by treatment arms.

Based upon laboratory normal ranges, the laboratory test results will be categorized according to the normal range provided by local lab as: “low” (below the lower limit), “normal” (within the normal range) and “high” (above the upper limit). The shift on worst-case post-baseline categories of laboratory result from baseline for each parameter will be summarized by visit in a table.

Laboratory results including hematology, coagulation, clinical chemistry and urinalysis will be graded as Grade 0, 1, 2, 3 or 4 based on Division of AIDS (DAIDS) criteria listed in [Appendix 1](#). The increases on maximum grades will summarized by visit for each parameter. Furthermore, for each parameter of hematology, coagulation and clinical chemistry, the shift of post-baseline maximum grade from baseline will be summarized by visit and overall worst case postbaseline.

SI units will be used for clinical laboratory summary tables and listings. Participants who had shifts from baseline will be listed, along with flags to indicate the abnormalities (“low” and “high”). Laboratory evaluations will be based on GSK Core Data Standards. The details of the planned displays are provided in the OPS Section 2, List of Data Displays/ TFL Table of Content.

Electrocardiograms

ECG data will include heart rate, PR, QRS, QT, and corrected QT (QTc). The QTc data analysis will use the collected values based on Fridericia formula.

ECG findings are defined from best to worst as: “normal”, “abnormal - not clinically significant”, and “abnormal - clinically significant”. The worst finding will be selected at each time point when there is repeat ECG. All ECG findings will be summarized for screening visit. In addition, the QTcF values will be summarized in a table by categories of “≤ 450 msec”, “451-480 msec”, “481-500 msec”, “≥ 501 msec”, and “missing”. Worst -case post baseline of QTcF values is calculated as the maximum assessment of each “QTcF Interval, Aggregate (msec)”.

A listing of ECG values for participants with abnormalities of potential clinical importance will be provided. In addition, clinically significant ECG findings will be listed in a separate listing.

Extent of Exposure

Listings of data on participant exposure will be generated for each treatment arm.

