5.2. Exclusion Criteria

Participants are excluded from the study if any of the following criteria apply:

Medical Conditions

- 1. History or presence of cardiovascular, respiratory, hepatic, renal, gastrointestinal, endocrine, hematological, or neurological disorders capable of significantly altering the absorption, metabolism, or elimination of drugs; constituting a risk when taking the study intervention or interfering with the interpretation of data.
- 2. Abnormal BP as defined as greater than 140 mm/Hg systolic, greater than 90 mm/Hg diastolic, or less than 90 mm/Hg systolic at Screening. BP at Screening is the average of 3 BP readings taken using the methods described in Section [8.3.2](#).
- 3. Known hypersensitivity to any constituent present in the investigational product or history of severe hypersensitivity or anaphylaxis after receiving a COVID-19 vaccine.
- 4. Clinically significant multiple or severe drug allergies, intolerance to topical corticosteroids, or severe post-treatment HSRs (including, but not limited to, erythema multiforme major, linear immunoglobulin A [IgA] dermatosis, toxic epidermal necrolysis, and exfoliative dermatitis).

5. Lymphoma, leukemia, or any malignancy within the past 5 years except for basal cell or squamous epithelial carcinomas of the skin that have been resected with no evidence of metastatic disease for 3 years.
6. For Part A and Part B, any condition that would prohibit receipt of IM injections in the investigator's opinion, such as coagulation disorder, bleeding diathesis, or thrombocytopenia.
7. Breast cancer within the past 10 years.
8. Alanine aminotransferase (ALT) $>1.5 \times$ upper limit of normal (ULN).
9. Total bilirubin $>1.5 \times$ ULN (isolated total bilirubin $>1.5 \times$ ULN is acceptable if total bilirubin is fractionated and direct bilirubin $<35\%$).
10. Current or chronic history of liver disease or known hepatic or biliary abnormalities (with the exception of Gilbert's syndrome or asymptomatic gallstones).
11. Participants exposed to an individual known to be infected with COVID-19 by PCR testing within the 14 days prior to Screening.
12. QT interval corrected using Fridericia's formula (QTcF) >450 msec.

Prior/Concomitant Therapy

13. Use of any over-the-counter or prescription medications within 7 days (or 14 days if the drug is a potential enzyme inducer) or 5 half-lives (whichever is longer) prior to dosing until completion of the follow-up visit, unless permitted in Section 6.8.

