4.1.2. Baseline and Post-Baseline Definition

For all endpoints (except for electrocardiogram [ECG]) the baseline value will be the latest pre-dose assessment with a non-missing value on or after Day -1 visit, including those from unscheduled visits. For ECG endpoints, which pre-dose measurements are only planned at Screening visit, the baseline value will be the most recent pre-dose assessment with non-missing value before Day 1 visit, including unscheduled visits. If triplicate 12-lead ECGs are collected at the last pre-dose assessment, the average of the

three measurements will be used as baseline record. If time is not collected, Day 1 assessments are assumed to be taken prior to first dose and used as baseline. If triplicate 12-lead ECGs are collected at any post-baseline visit, the average of the three measurements will be calculated and used in derivation of summary statistics.

Unless otherwise stated, if baseline data is missing no derivation will be performed and baseline will be set to missing.

Post-Baseline is defined as an occurrence after first dose of the treatment on Day 1.

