6.2.5. Multiple measurements at One Analysis Time Point

During screening and during post-baseline visits, triplicate ECG assessments may be taken. Mean of the measurement will be calculated first and recorded. Summary statistics will be based on the recorded mean. This will apply to both baseline and post baseline assessments.

For lab tests on a study day, if more than one assessment is taken on the same day, the test from a central lab will be taken over the test from a local lab. If multiple assessments are taken from the same type of lab, the worst case will be used.

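### SAP 6.2.3 places some reportable laboratory values in both Grade 0 and Grade 1, and the QTcF categories have no place for unrounded triplicate means

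*SAP*

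**What the plan says.** **QTcF.** In the ECG part of SAP 4.3.2.3, "the QTcF values will be summarized in a table by categories of “≤ 450 msec”, “451-480 msec", and the list ends with "481-500 msec”, “≥ 501 msec”, and “missing". The same section takes the worst case from a stored aggregate: "Worst -case post baseline of QTcF values is calculated as the maximum assessment of each “QTcF Interval, Aggregate (msec". SAP 6.2.5 says how that aggregate arises from triplicates: "Mean of the measurement will be calculated first and recorded. Summary statistics will be based on the recorded mean". SAP 4.1.2 says the same for post-baseline triplicates: "the average of the three measurements will be calculated and used in derivation of summary statistics". Neither section states a rounding rule or a number of decimals.

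**Laboratory grades.** SAP 4.3.2.3 grades results 0 to 4 by the table in SAP 6.2.3 and reports grade increases and shifts from baseline. It also states that "SI units will be used for clinical laboratory summary tables and listings". Most rows of the table print limits in two units, conventional first and SI second.

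**The concern.** A category table should put each value in exactly one cell. Here some laboratory values meet two grades, and some averaged QTcF values may meet no category.

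The laboratory overlap matters because the displays count changes in grade. Suppose baseline sodium is clearly normal and a later result is 146 mmol/L. A program that tests Grade 0 first shows no change; one that tests Grade 1 first shows an increase. The effect also runs the other way. If baseline is 146 and a later value is above 146 but below 150, the first program counts an increase and the second does not. Two programmers who both follow the SAP could therefore produce different tables.

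The QTcF gaps lie just above 450, 480 and 500 msec, the cuts that such a table exists to display.

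**Working it through.** There is no stated figure to reproduce, because the question is whether the printed intervals are complete and do not overlap. Each interval was read with its printed open or closed ends, and values at and between the cut-points were tested for membership.

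**Laboratory rows with a shared closed end point (SAP 6.2.3)**

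| Test | Grade 0 | Grade 1 | Value in both |
|---|---|---|---|
| Sodium, high, mmol/L | ≤146 | 146 to <150 | 146 |
| Potassium, high, mmol/L | ≤5.6 | 5.6 to <6.0 | 5.6 |
| Hemoglobin, male, g/dL | ≥10.9 | 10.0 to 10.9 | 10.9 |
| Hemoglobin, male, mmol/L | ≥6.76 | 6.19 to 6.76 | 6.76 |
| Hemoglobin, female, g/dL | ≥10.4 | 9.5 to 10.4 | 10.4 |
| Hemoglobin, female, mmol/L | ≥6.48 | 5.88 to 6.48 | 6.48 |
| Neutrophils, x10^9/L | ≥1.000 | 0.800 to 1.000 | 1.000 |
| WBC, x10^9/L | ≥2.499 | 2.000 to 2.499 | 2.499 |

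The neutrophil and WBC rows show the same overlap in cells/mm³. For sodium and potassium the mEq/L line of the same cell reads <146 and <5.6. These ions carry a single charge, so mEq/L and mmol/L are the same number and the two lines contradict each other. All five tests are in the required panel (Protocol Table 13, SAP Table 12). Lymphocytes, low calcium and high potassium in mEq/L show no gap or overlap, so the problem is not a general feature of how the table was extracted.

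Two rules might look like a tie-break. The maximum grade in SAP 4.3.2.3 and the worst-case rule for same-day repeats in SAP 6.2.5 both choose among several results. Neither says which grade one result takes.

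**QTcF.** The mean of three whole-msec readings is a multiple of one third. All such means from 440 to 510 msec were tested. Every whole number falls in exactly one category. Six means fall in none: 450.33, 450.67, 480.33, 480.67, 500.33 and 500.67. For example, (450 + 450 + 451)/3 = 450.33. Rounding to the nearest msec would place them all, but 450.33 would then go to ≤450 and 500.33 to 481-500, although each exceeds its threshold.

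**How many records.** The documents give no distributions, so the following are assumptions.

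- Sodium reported in whole numbers, mean 140 mmol/L, SD 1.5, 2 or 2.5. P(145.5 < x < 146.5) = 0.0001, 0.0024 or 0.0092. With 200 participants and eight post-dose draws each (an assumed count), 200 × 8 = 1,600 results, of which about 0.2, 4 or 15 equal 146.
- QTcF with mean and SD of 405 and 18, 410 and 20, or 415 and 20 msec. P(450 < x < 451) = 0.0009, 0.0026 or 0.0041. Two of every three possible means in that interval have no category, so multiplying by 2/3 gives 0.6, 1.7 or 2.7 per 1,000 triplicate means. A rate is shown because the number of post-dose triplicates cannot be read reliably from the schedule.

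**The case against.** **The QTcF gap is conditional.** The categories suit whole-msec values. SAP 6.2.5 speaks of a recorded mean without giving its precision, and display details are left to the Output and Programming Specification, which is not available here. If the stored aggregate is a whole number, nothing is lost. This stands: the gap exists only if decimals are kept. The SAP should still settle it, because rounding moves some values to the wrong side of a threshold.

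**The intended grades can be inferred.** The DAIDS extract in Protocol Table 14 has Grades 1 to 4 only, so Grade 0 reads naturally as not reaching Grade 1. The mEq/L lines show the intended sodium and potassium cuts. This is fair and shows which way to correct the table. It is not a written rule for the value itself, at baseline or later.

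**Stronger readings are not supported.**

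- A reader might infer that these values disappear from the report. They do not: the summary statistics still use the mean, and listings of ECG and laboratory findings are planned.
- A reader might infer that the endpoint on laboratory abnormalities in SAP 4.3.2.2 changes. That endpoint concerns clinically significant abnormalities. Protocol 8.3.4 has the investigator record clinically significant changes as AEs, and SAP 6.2.3 notes that an out-of-range value need not be of clinical concern.
- A reader might point to a screening mean of 450.33. Exclusion criterion 12 bars "QT interval corrected using Fridericia's formula (QTcF) >450 msec", Protocol Section 5 permits no waivers, and the Safety set requires exposure, so that value should not reach the table.
- A reader might add the laboratory gaps, such as sodium between 120 and 121. They lie between values at usual reporting precision. The albumin overlap concerns a test outside the routine panel.

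**Conclusion.** The point holds as a table correction of limited reach. The laboratory overlaps are certain from the printed text. Sodium 146, potassium 5.6, hemoglobin 10.9 and 10.4 g/dL and neutrophils 1.00 are ordinary reportable values; WBC 2.499 needs finer reporting than is usual. The QTcF gap depends on the averaged value being kept unrounded, which the SAP neither requires nor rules out.

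The effect is confined to a few records in descriptive grade-increase, grade-shift and QTcF category tables. Post-baseline ECGs are scheduled in Part C only, so the post-baseline QTcF effect arises only there. The primary PK analysis, the AE analyses, investigator-judged abnormalities and the low/normal/high shift table against laboratory ranges are unaffected. The record counts rest on assumed distributions and show only that the number is small; the sodium range is wide for that reason.

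**What to change.** 1. In SAP 4.3.2.3 use QTcF categories ≤450, >450 to ≤480, >480 to ≤500 and >500 msec, plus missing. Every mean tested from 440 to 510 msec then falls in exactly one category, with or without rounding.
2. In the SI line of SAP 6.2.3 set Grade 0 to <146 for high sodium and <5.6 for high potassium, matching the mEq/L line.
3. Make the Grade 0 end point open in both unit lines for hemoglobin (male >10.9 g/dL and >6.76 mmol/L; female >10.4 g/dL and >6.48 mmol/L), neutrophils (>1,000 cells/mm³ and >1.000 x10^9/L) and WBC (>2,499 cells/mm³ and >2.499 x10^9/L).
4. Add one sentence: a value meeting two grades takes the higher grade, at baseline and post-baseline, and values are graded at reported precision.

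The cost is a few table cells and one line of code. A handful of boundary values may be shown as Grade 1 instead of Grade 0.

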8. STUDY ASSESSMENTS AND PROCEDURES

- Study procedures and their timing are summarized in the SoA (Section 1.3). Whenever vital signs, 12-lead ECGs, and blood draws are scheduled for the same nominal time, the assessments should occur in the following order: vital signs, 12-lead ECG, blood draws. The timing of the assessments should allow the blood draw to occur at the exact nominal time. The actual time of assessment or procedure must be reported in the eCRF.
- Protocol waivers or exemptions are not allowed.
- Immediate safety concerns should be discussed with the Medical Monitor immediately upon occurrence or awareness to determine if the participant should continue or discontinue study intervention.
- Adherence to the study design requirements, including those specified in the SoA (Section 1.3), is essential and required for study conduct.
- All screening evaluations must be completed and reviewed to confirm that potential participants meet all eligibility criteria. The investigator will maintain a screening log to record details of all participants screened and to confirm eligibility or record reasons for screening failure, as applicable.

- CC1

- Procedures conducted as part of the participant's routine clinical management (e.g., blood count) and obtained before signing of ICF may be utilized for screening or baseline purposes provided the procedure met the protocol-specified criteria and was performed within the timeframe defined in the SoA (Section 1.3).
- The maximum amount of blood collected from each participant over the duration of the study, including any extra assessments that may be required, will not exceed 500 mL. Typical blood volumes expected during the usual course of study participation will be approximately 150 mL.
- Repeat or unscheduled samples may be taken for safety reasons or for technical issues with the samples.

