6.2. Appendix 1 Data Derivations Rule

6.2.1. Change from Baseline

The change from baseline will be calculated by subtracting the baseline values from the individual post-baseline values. If either the baseline or post-baseline value is missing, the change from baseline is set to missing as well.

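### The QTcF table described for Part C uses only absolute bands whose lowest band is the entry range, and no ECG display is assigned the change from baseline

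*SAP*

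**What the plan says.** The Electrocardiograms paragraph of SAP 4.3.2.3 states that "the QTcF values will be summarized in a table by categories of" 450 msec or below, 451–480, 481–500, 501 or above, and missing. It also says that the worst "case post baseline of QTcF values is calculated as the maximum assessment of each" aggregate QTcF interval, which is a maximum value and not a maximum change. ECG findings (normal, abnormal, clinically significant) are to be summarized for the screening visit. Two listings complete the paragraph. One is described as follows: "A listing of ECG values for participants with abnormalities of potential clinical importance will be provided". The other covers clinically significant findings. The SAP gives no criteria for potential clinical importance.

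Protocol 5.2, criterion 12, excludes a "QT interval corrected using Fridericia's formula (QTcF) >450 msec", and Protocol Section 8 adds: "Protocol waivers or exemptions are not allowed".

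The pieces needed for a change analysis are already in the SAP:

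- Section 4.1.2 defines an ECG baseline: "the baseline value will be the most recent pre-dose assessment with non-missing value before Day 1 visit", averaged if taken in triplicate.
- Section 6.2.5 bases ECG summary statistics on the triplicate mean, both at baseline and afterwards.
- Section 6.2.1 gives a general rule: "The change from baseline will be calculated by subtracting the baseline values from the individual post-baseline values".

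The Part A schedule marks a 12-lead ECG at Screening only. The Part C schedule marks ECGs at further time points.

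**The concern.** The lowest reporting band coincides with the range in which participants may enter. The table can therefore register an increase only when a healthy participant crosses 450 msec. Someone going from 380 to 445 msec appears exactly as someone who did not change.

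Part C gives a dose and infusion rate that Protocol 2.3.1 describes as not used before. It has no control arm, so each participant's own baseline is the only internal reference for a post-dose ECG. If the QTcF table were read alone, sizeable individual increases could pass unremarked.

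The contrast within SAP 4.3.2.3 suggests an omission. Vital signs and laboratory data both receive change-from-baseline summaries and shift tables; ECG receives neither. The general rule in SAP 4.1.1 does not close the gap, because it applies descriptive statistics to the endpoints in Section 1.1, and ECG is not among them.

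**Working it through.** **Plan's own figure.** The documents give no QTcF-specific figure. The nearest is the detection statement for Part C Cohort 1 (Protocol 9.5, SAP Section 5): with 200 participants, a 90% chance of at least one event at a true rate of 1.14%. Check: 1 − (1 − 0.0114)^200 = 0.899. It reproduces.

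**Step 1: what the table cannot show.** Inputs are the entry limit of 450 msec (Protocol 5.2) and the top of the lowest band, 450 msec (SAP 4.3.2.3). A rise r leaves a participant in the lowest band when baseline + r ≤ 450, so the largest unseen rise is 450 − baseline. This needs no outside assumption.

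| Baseline (msec) | Largest rise still in lowest band (msec) |
|---|---|
| 380 | 70 |
| 390 | 60 |
| 400 | 50 |
| 410 | 40 |
| 420 | 30 |
| 440 | 10 |
| 450 | 0 |

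A 31 msec rise is unseen from any baseline up to 450 − 31 = 419, and a 61 msec rise from any baseline up to 450 − 61 = 389.

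**Step 2: what share of rises that is.** This needs the baseline QTcF distribution, which the documents do not give. Assume it is normal with mean μ and SD σ, truncated at 450, and that the rise does not depend on baseline. Then

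share unseen = Φ((450 − r − μ)/σ) / Φ((450 − μ)/σ).

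| Assumed mean | Assumed SD | 31 msec rise unseen | 61 msec rise unseen |
|---|---|---|---|
| 380 | 15 | 99.5% | 72.6% |
| 380 | 25 | 94.3% | 64.2% |
| 400 | 15 | 89.8% | 23.2% |
| 400 | 20 | 83.4% | 29.3% |
| 400 | 25 | 79.4% | 33.8% |
| 420 | 15 | 48.4% | 2.0% |
| 420 | 25 | 54.7% | 12.1% |

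Over means of 380–420 and SDs of 15–25, the range is about 48–99.5% for a 31 msec rise and 2–73% for a 61 msec rise.

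**Step 3: effect on seeing at least one case.** Suppose, for illustration, that 1.14% of 200 participants had a 61 msec rise. A change table shows at least one with probability 0.899. If a share h is unseen, the absolute table shows at least one with probability 1 − (1 − 0.0114(1 − h))^200:

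- h = 0.07: 0.881
- h = 0.29: 0.803
- h = 0.69: 0.507

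**The case against.** A reader might infer that Part C could report no QTcF effect at all, that the baseline ECG goes unused, or that most large rises are hidden. The documents do not support those readings.

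- **Continuous summaries are foreseen.** SAP 4.1.2 and 6.2.5 say that triplicate means feed ECG summary statistics at baseline and after it. A shift in the mean could be seen there even if nobody crossed 450 msec. The change rule in 6.2.1 does not exclude ECG.
- **There are other routes to detection.** SAP 4.3.2.3 plans two ECG listings. Under Protocol 10.3.1, a clinically significant ECG abnormality, including a worsening from baseline, is an AE, and AE incidence is the primary endpoint of Part C.
- **The OPS has not been seen.** The SAP sends much display detail there. A change table, or a change criterion for potential clinical importance, may already exist in it.
- **ECG is not an endpoint.** It is absent from SAP 1.1, and neither the risk table in Protocol 2.3.1 nor the AESI list in 8.4.7 names a QT risk.
- **Many of the largest rises would show.** With an assumed mean of 400 and SD of 20, about 71% of 61 msec rises leave the lowest band.

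All of this stands, and it limits the point. It does not remove it: the SAP text assigns the change from baseline to vital signs and laboratory data and to no ECG display, and the arithmetic in Step 1 holds whatever the baseline distribution.

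**Conclusion.** The point holds in a narrow form. The only categorical QTcF display that the SAP describes is blind to any within-person rise no larger than 450 minus baseline, and no ECG display is told to use the change from baseline.

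The size is uncertain. The ranges in Step 2 rest on assumed baseline distributions and are too wide to support a single figure. They show that the table would miss roughly half to nearly all 31 msec rises, and anywhere from very few to nearly three quarters of 61 msec rises.

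Two further limits apply. The 450 msec limit acts at eligibility, so a later pre-dose ECG taken as baseline could exceed it. The footnote giving the Part C ECG times is missing from the text available here, so the number of post-dose ECGs could not be confirmed.

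This is a gap in a supportive, descriptive safety display. It does not affect the primary analysis or any listed endpoint, but it is worth closing because the remedy is nearly free.

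**What to change.** In SAP 4.3.2.3, for Part C:

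1. Add QTcF change from baseline at each post-dose ECG time point: n, mean, SD, median, minimum, maximum and a 95% CI, which is the SAP's default level (4.1.1).
2. Beside the absolute bands, add a table of the maximum post-baseline increase by category, for example 30 or less, above 30 to 60, and above 60 msec. These cut-offs are illustrative and do not come from the documents; the sponsor should set and state its own.
3. Use the baseline in 4.1.2 and the triplicate means in 6.2.5 for both.
4. Note with the second table that, without a control arm, the maximum increase over repeated ECGs also contains random variation, so counts in the upper categories are not all drug effect.

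If the OPS already contains such displays, a sentence in 4.3.2.3 naming them is enough.

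Cost: two summaries programmed from data already scheduled, with baseline and change derivations already defined. No new procedure, visit or sample is needed, and no existing display has to be altered.
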